All data will be de-identified before it is entered into a redcap database at the JJPVA, Philadelphia VA, Northport VA, and Central Texas VA over the intranet. All principal analyses will be conducted based on the intention-to-treat principle. Linear mixed models will be used to examine changes in primary and secondary outcomes for Veterans over time and to examine whether the effects of PLF and TAU on these outcomes vary with time adjusted for the time-dependent treatment, covariates of interest and imbalanced baseline prognostic factors, using data reduction methods as appropriate. *For the PLF subjects, individual's random effect will be nested within the group they are assigned to, while for TAU subjects, they will be nested within the clinician effect.* All data will be entered into an SPSS database at the JJPVA constructed by the data manager. Tenets of our data system include double data entry, range checks and exclusion of identifiers that can be directly traced to individuals. Preliminary analyses will include computing descriptive statistics and inspecting features and patterns of data to determine whether data transformations are needed. Quantitative measures will be graphed and their distribution inspected for any outlier value, which will be winsorized. All principal analyses will be conducted based on the intent-to-treat principle, that is, all Veterans with data will be included, regardless of the actual treatment received. For subjects who drop out during the study, their data up to that point will be used, but not carried forward to subsequent time points. We will also conduct an economic cost analysis of the Project Life Force intervention to compare cost effectiveness of telehealth groups versus the in-person groups pre-COVID. We will use an implementation science framework, The Consolidated Framework for Implementation Research, to determine barriers and facilitators of the telehealth-delivered PLF safety planning intervention. Development of the script and qualitative analysis will be conducted by [name]; a qualitative and implementation expert.

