Analyses to Determine Generalizability of Results: We will compare the baseline characteristics (e.g., age, sex, education) of the study population to those that declined participation, and will evaluate reasons for refusal that will be tracked. A sensitivity analysis using the propensity score methodology would be applied if those who refuse participation were significantly different on important measures from the participants. Missing data and loss to follow-up are usually concerns in longitudinal studies presenting problems in interpretation. The validity of the resulting inferences depends critically on the underlying mechanism that generates the missing observation- MAR, MCAR or MNAR.⁴⁴ Both survival analysis and mixed-effect models, the proposed

statistical methodology, can handle data that is missing at random or missing completely at random; that is, if the mechanism for missing data does not depend on the value of the response variable, given the information in the predictor variables already in the model (treatment condition and baseline scores), then no further adjustment is necessary.

However, when missing data are related to outcomes of interest even after conditioning on the known data (i.e. treatment condition), such as when in some patients side-effects of the active treatment affect the suicidal behavior risk and also cause drop-out, parameter estimates and resulting

tests of hypotheses will be biased, and this can affect the generalizability as well as the reproducibility of the results. To address this problem, we will look for patterns of missingness. For example, data will be stratified according to their missing pattern (e.g., early and late termination, and incomplete follow-up); and, assuming a monotonic missingness pattern applies, we will use Diggle methodology, allowing us to examine the effects of missing-data patterns on outcome measures. We will explore other patterns using the techniques referenced above.

b. Provide power analysis or describe how sample size was determined:

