Title: **Group ("Project Life Force") vs. Individual Suicide Safety Planning RCT**

NCT Number: **NCT03653637**

Date: **05/12/2025**

Primary Statistical Analysis Plan

The primary outcome of suicidal behavior will be analyzed using a Cox Proportional Hazard Regression, with treatment condition (PLF+TAU vs. TAU) and baseline suicidal behavior level as predictors, and incidence and time to the first suicidal behavior during the study course as the outcome variables. The model will adjust for treatment site. Kaplan-Meier estimates of the cumulative hazard function for both groups will be graphed and the proportionality assumption checked. If the hazard functions are not proportional, the non-parametric log-rank test will be used instead, with treatment condition as predictor, and we will use a sensitivity analysis to test the effect of baseline suicidal behavior severity by splitting the treatment conditions by the presence/absence suicidal behavior.

Most secondary and other outcomes (depression, hopelessness, thwarted belongingness, aggression dimensions, insomnia and suicide-related coping) will be analyzed in Linear Mixed Effects (LME) regression models. All LMEs will be adjusted for site and will include randomization condition, time, and a randomization by time interaction. The treatment effect of PLF+TAU vs TAU will be the treatment by time interaction. Time will be treated as a linear variable. Mixed-effect models can be fit to data with dropout or missing values as long as the data is missing at random, thus, attrition does not necessarily reduce the number of participants included in these analyses.

For the two outcomes (drug and alcohol use) that are only measured at the one-year follow-up (with retrospective questions about the past 12 months), we will compare between PLF+TAU and TAU with t-tests or Mann-Whitney U tests where appropriate.

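### The mixed models do not use the fact that randomised arms share a baseline mean, which costs precision but does not cause bias, and the protocol and SAP differ on how baseline scores enter

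*SAP*

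**What the plan says.** The SAP assigns "Most secondary and other outcomes (depression, hopelessness, thwarted belongingness, aggression dimensions, insomnia and suicide-related coping") to linear mixed models. All are adjusted for site and "will include randomization condition, time, and a randomization by time interaction". It adds that "The treatment effect of PLF+TAU vs TAU will be the treatment by time interaction" and that "Time will be treated as a linear variable". No baseline score is named as a covariate for these models, and nothing constrains the arms to a common baseline mean. The SAP does not say whether the baseline visit is one of the modelled outcomes, and it does not give the within-person random effects.

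Two other parts of the SAP differ from this. The Cox model for suicidal behavior takes treatment condition and "baseline suicidal behavior level as predictors". "For the two outcomes (drug and alcohol use) that are only measured at the one-year follow-up", the SAP plans t-tests or Mann-Whitney tests.

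The protocol reads differently. Section 17.a plans mixed models adjusted for "covariates of interest and imbalanced baseline prognostic factors". Its paragraph on missing data relies on "predictor variables already in the model (treatment condition and baseline scores"). The table in section 13.b schedules the relevant scales at 0, 3, 6 and 12, four times each. Section 13 assigns half the participants to PLF by randomisation.

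**The concern.** Suppose the month-0 score is the first of four repeated outcomes. The randomization-condition term is then the arm difference at time 0. Under randomisation its true value is zero, yet the model spends information estimating it. Chance imbalance at baseline is subtracted in full from the later difference, much as in a comparison of change scores, instead of in proportion to how well baseline predicts follow-up.

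Precision on the mixed-model outcomes is at stake. The protocol's sample size was set for suicidal behavior alone, and neither document states power for depression, hopelessness, insomnia or the other scales. The baseline scores that would recover some precision are already scheduled.

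There is also a question of specification. An analyst following the SAP would fit one model, and an analyst following protocol section 17.a could reasonably fit another.

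**Working it through.** **The plan's own figure.** There is none on this point. The only sample-size result, N=145 in protocol section 17.b, is for the survival analysis.

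**Inputs from the documents.** Visits at 0, 3, 6 and 12. The table gives no unit, and months are taken from the SAP's one-year follow-up and the 12-14 month participation. Allocation is 1:1. The fixed effects are as in the SAP.

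**Assumptions.** Month 0 is in the outcome vector. Data are complete. Variance σ² is equal at each visit. The within-person correlation ρ is not given, so a range is shown. Group and clinician clustering (protocol 17.a) is ignored.

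**Step 1: slope difference, compound symmetry.** For the visit times, Σt = 21, Σt² = 189 and Σ(t − 5.25)² = 189 − 21²/4 = 78.75. Up to a common factor N/(4σ²(1 − ρ)), the information on the arm-by-time coefficient is:

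- with the arm main effect (SAP model): 78.75
- without it (common baseline mean): 189 − 441ρ/(1 + 3ρ)

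The variance ratio is the first divided by the second, and the SE cut is 1 minus its square root.

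| ρ (assumed) | 189 − 441ρ/(1 + 3ρ) | Variance ratio | SE cut |
|---|---|---|---|
| 0.3 | 119.4 | 0.660 | 19% |
| 0.5 | 100.8 | 0.781 | 12% |
| 0.7 | 89.4 | 0.881 | 6% |
| 0.9 | 81.7 | 0.964 | 2% |

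At ρ = 0.5 the SE is 1/√0.781 = 1.13 times larger under the SAP model. Taking a two-sided 5% test (alpha is not stated), an effect with 80% power under the common-baseline model lies 2.80 standard errors from zero. Under the SAP model it lies 2.80/1.13 = 2.48 away, and Φ(2.48 − 1.96) gives about 70% power. With 20% monotone dropout the SE ratio at ρ = 0.5 is 1.12 instead of 1.13.

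**Step 2: other covariance structures.** The same calculation was run with a random intercept and slope: baseline variance 1, intercept share 0.4 to 0.8, slope SD 0.3 to 0.8 over 12 months, and intercept-slope correlation −0.3 to 0.3. The SE ratio ran from 1.00 to 1.22, a cut of 0% to 18%. Widening the intercept-slope correlation to ±0.5 raised the top of the range to about 23%. The cut is close to nil when the intercept share is high and the intercept-slope correlation positive. With first-order autoregressive correlation of 0.5 to 0.8 over three months, the ratio is 1.42 to 1.19.

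**Step 3: month-12 difference with categorical time.** In units of 4σ²/N, the variance is 2(1 − ρ) with the arm main effect and 1 − ρ² with a common baseline mean. The ratio is (1 + ρ)/2, which gives SE cuts of 19%, 13% and 8% at ρ = 0.3, 0.5 and 0.7.

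A comparison with the SAP's linear model is also useful. Twelve times its slope has variance 144(1 − ρ)/78.75 = 1.829(1 − ρ), so the ratio is (1 + ρ)/1.829 = 0.711, 0.820, 0.930 and 1.039 at ρ = 0.3, 0.5, 0.7 and 0.9. The SE changes by −16%, −9%, −4% and +2%. Dropping linearity therefore gives back part of the gain, and all of it at very high correlation.

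**Step 4: what a common baseline does when time stays linear.** Take an arm difference of 0, 1, 1, 1 at the four visits, that is, an early effect that plateaus. The SAP model's slope is (−2.25 + 0.75 + 6.75)/78.75 = 0.0667, which implies 12 × 0.0667 = 0.80 at month 12. The constrained linear model's slope is [21 − 63ρ/(1 + 3ρ)] / [189 − 441ρ/(1 + 3ρ)], which implies 1.11, 1.00 and 0.91 at ρ = 0.3, 0.5 and 0.7. The answer then depends on a nuisance correlation.

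**The case against.** The best defence is that arm, time and arm-by-time is a standard and valid longitudinal model. Under randomisation its interaction is not biased by the free baseline term, and the test keeps its size. The primary Cox model already adjusts for baseline, and no stated power claim for the mixed-model outcomes is undermined. All of this stands. The point is about efficiency in secondary and other outcomes.

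It can also be said that protocol section 17.a already has baseline scores in the model. If they were covariates, with only later visits as outcomes, the precision loss would not arise. That stands too, but the SAP's list of terms does not include them, so the wording still has to be reconciled.

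A reader might infer four stronger things that the documents do not support:

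- **That baseline data are thrown away.** If month 0 is in the outcome vector, it informs the slopes. Only the equality of the baseline means goes unused.
- **That every secondary effect is affected.** The SAP says most, and drug and alcohol use are compared from a single measurement.
- **That the loss has a known size, or is always material.** No correlation, variance or random-effects structure is given, and in some random-slope settings the loss is practically zero.
- **That simply deleting the arm main effect is free of cost.** Step 4 shows otherwise when time stays linear. Ten weekly sessions followed by follow-up to month 12 make a non-linear effect plausible.

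**Conclusion.** The point holds as a loss of precision and a gap in specification. As written, the mixed models contain a free baseline difference between randomised arms and make no other use of baseline, while the protocol describes baseline scores as being in the model. If month 0 is time 0, a common baseline mean would reduce the SE of the slope difference by 19%, 12%, 6% or 2% at assumed compound-symmetry correlations of 0.3, 0.5, 0.7 or 0.9, and by about 0% to about 20% with random slopes. In none of the settings examined did the constraint raise the SE of the same contrast.

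These sizes rest on assumed covariance structures, complete data unless stated, and no group or clinician clustering. They do not apply if baseline was meant as a covariate with only post-baseline outcomes. In that case the SAP has left the covariate out of its description. The change is worth making, but the validity of the planned test does not depend on it.

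**What to change.** 1. State in the SAP whether the month-0 score enters the mixed models as an outcome or as a covariate, and bring the SAP and the two statements in protocol section 17.a into agreement.
2. For the mixed-model outcomes, specify one of the following, with site:
   - the baseline score as a covariate, with months 3, 6 and 12 as outcomes; or
   - all four visits as outcomes, time as a category, arm-by-time terms and no arm main effect, so that the arms share a baseline mean.
3. Report the month-12 difference as the treatment effect. Do not pair the common-baseline constraint with linear time alone, because the arm difference would then be forced along a straight line from zero.
4. If unblinded results have already been seen, keep the planned model as the main analysis and report the new one as a labelled sensitivity analysis.

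The cost is a few sentences of SAP text and a small change of model code, with no new data. The price of categorical time is that part of the precision gain is given back, and at a correlation near 0.9 the month-12 SE is about 2% larger than under the SAP's linear model. In return, the month-12 estimate does not depend on the effect being linear.

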Interpersonal Needs Questionnaire	Research office	[name], [name]	0, 3, 6,12	4
Mini-International Psychiatric interview (MINI)	Research office	[name], [name]	0	1
McLean Screening	Research office	[name],	0	1

Instrument for BPD		[name]		
PLF Intervention Sessions	Research office	[name]	Weekly	10
Moral Injury Outcome Scale (MIOS)	Research office	[name], [name]	0, 3, 6, 12	4

c. If laboratory tests are part of this protocol, will some or all study-related tests be performed outside this medical center?

YES	NO	N/A	X
-----	----	-----	---

d. Provide a statement that defines who will be financially responsible for the costs associated with participation in the study (e.g., examinations, procedures, drugs, devices, etc.) and a statement that defines what will be provided without cost to the subjects:

The patient will not incur any costs from participating in this study. The PLF intervention will be provided free of charge. In the event of an injury resulting from the research study the facilities of the Bronx VA will be made available to patients.

List all Authorized Prescribers of drugs (whether or not the drug is investigational)

NA

e. VHA Health Record (If yes to (i) below or if clinical resources are to be used, a VHA health record must be created in CPRS [VHA Handbook 1200.05 #29j]).

(i) Will the research intervention possibly lead to physical or psychological adverse events?

YES	X	NO	
-----	---	----	--

(ii) Do you have a process in place to include a copy of the signed informed consent and HIPAA authorization in the medical record for the type research described above for each subject?

YES	X	NO	
-----	---	----	--

If yes, Please describe: **A copy of each consent is scanned into subjects' charts and a hard copy is retained in study records.**

(iii) Did the IRB determine that CPRS flagging is required?

YES	NO	X	
-----	----	---	--

14. Risks:

a. Identify study risk:

No Risk	
Minimal Risk	
Greater Than Minimal Risk	X

b. Describe the steps you could take to minimize risk to subjects, *without changing the science* of the study:

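### Drug and alcohol use at one year are compared without the site adjustment used in the Cox and mixed models, by a test that is not yet chosen

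*SAP*

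**What the plan says.** The SAP's last paragraph deals with drug and alcohol use separately: "For the two outcomes (drug and alcohol use) that are only measured at the one-year follow-up", by questions that look back over the preceding year, "we will compare between PLF+TAU and TAU with t-tests or Mann-Whitney U tests where appropriate". It states no site term, no covariate, no rule for choosing between the two tests and no method for missing values.

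Elsewhere the SAP does use site. Of the Cox model for suicidal behavior it says "The model will adjust for treatment site", and of the mixed models "All LMEs will be adjusted for site". If hazards are not proportional, however, "the non-parametric log-rank test will be used instead, with treatment condition as predictor", and no site term is stated there.

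In the protocol, item 17.a plans adjustment for selected covariates and for prognostic factors out of balance at baseline. It takes intention-to-treat to cover each Veteran who contributes data, and it rules out carrying values forward. The table of procedures in item 13.b lists no instrument for drug or alcohol use at any visit. The MINI diagnostic interview is listed at time 0 only.

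**The concern.** Three things are left open for these two outcomes.

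- **Site.** The trial records site and adjusts for it in its main models. A plain two-sample test ignores it and gives up whatever precision it would bring.
- **Choice of test.** A t-test compares means; a Mann-Whitney test compares rank order. With skewed use data the two can answer differently. Without a stated rule, the hypothesis being tested depends on a choice made after the data are seen.
- **Missing values.** The SAP's argument about data missing at random concerns mixed models only. With one measurement and no carry-forward, a participant not assessed at one year drops out of the comparison.

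At stake are some precision and the pre-specification of two non-primary outcomes. The SAP does not say whether they count as secondary or other.

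**Working it through.** **Inputs.** From the SAP: one measurement at one year and no baseline value. From Protocol item 17.b: 145 participants and 20% dropout, both planning figures for the survival analysis and used here only for illustration. From Protocol item 13: half are allocated to each arm. My assumptions: two-sided 5% level, and site explaining 5% to 10% of the outcome variance. The documents give no figure for the latter.

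**1. The plan's own figure.** None is given for these outcomes. The only sample size, 145, belongs to the survival aim. I could not reproduce it as a total from its stated inputs: 49% falling by 35% to 31.9% is a hazard ratio of 0.569, which needs 100 events; 100 / 0.366 × 1.04 is about 285 with exponential dropout. That is a separate matter. Here 145 is only a headcount.

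**2. Terms stated for each analysis.**

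| Analysis | Site | Other baseline term |
|---|---|---|
| Cox model, first line | yes | baseline suicidal behavior |
| Log-rank fallback | none stated | none in the test itself |
| Mixed models | yes | none stated |
| Drug and alcohol use | none stated | none stated |

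**3. Precision from site.** Ratio of adjusted to unadjusted standard error = sqrt(1 − R²).

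- R² = 0.05: sqrt(0.95) = 0.975, a cut of 2.5%.
- R² = 0.10: sqrt(0.90) = 0.949, a cut of 5.1%.
- R² = 0: no gain.

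Estimating the site terms costs a little. Protocol item 17.a names four VA centers in connection with data entry. If those are the sites, there are k = 3 indicators. With n = 116 (step 4), the variance rises by about 1 + k/(n − k − 3) = 1 + 3/110 = 1.027, or 1.4% on the standard error. The net cut is then about 1.2% (0.975 × 1.014 = 0.988) to 3.8% (0.949 × 1.014 = 0.962).

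**4. Participants without a one-year value.** 0.20 × 145 = 29 missing, leaving 116, or 58 per arm. Detectable difference at 80% power = (1.960 + 0.842) × sqrt(2/n per arm):

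- all 145 (72.5 per arm): 2.802 × sqrt(2/72.5) = 0.465 SD;
- 116 (58 per arm): 2.802 × sqrt(2/58) = 0.520 SD for the t-test, and 0.520 / sqrt(0.955) = 0.532 SD for Mann-Whitney.

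Power for a 0.5 SD difference falls from 85.3% to 76.8%. For 10% to 40% missing, the t-test figure runs from 0.490 to 0.601 SD. Before the cost in step 3, site adjustment would take 0.520 to 0.520 × 0.975 = 0.507 or 0.520 × 0.949 = 0.493 SD.

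**5. Bias from missing values.** Suppose those missing differ from those observed by 0.5 SD in both arms. The bias is the difference in dropout times 0.5. At 20% in each arm it is 0. At 10% versus 30% it is 0.20 × 0.5 = 0.10 SD. These values are assumed.

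**6. Instrument.** The SAP describes retrospective questions at one year. The month-12 entries in item 13.b include no measure named for drug or alcohol use. The nearest candidates are a services log, which is scheduled at month 12, and the MINI, which is not.

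**The case against.** The strongest defense is that nothing here is invalid. With a single time point the arm-by-time mixed model cannot be fitted, and with no baseline value there is no baseline use to adjust for. A two-arm test is sound under randomization, and site adjustment is mainly a precision choice worth a few percent at best. All of that stands, and it is why this is a minor point.

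A reader might infer four stronger things. The documents support none of them.

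- *That these outcomes are treated unlike all the rest.* The log-rank fallback also has no site term. The mixed models are assigned to most secondary and other outcomes, with six domains listed, and some scheduled measures, such as reasons for living and impulsiveness, have no named method.
- *That intention-to-treat is broken.* Under the definition in item 17.a, comparing by arm everyone who has a one-year value complies. Nor is this a completers' analysis: a Veteran who stops treatment but attends at one year is included.
- *That the planned 20% dropout biases the result.* The protocol assumes it equal in both arms, and equal dropout does not by itself cause bias (step 5).
- *That no data will exist.* The SAP, dated after the protocol, says the questions are asked at one year. The table lists instruments, not items. What can be said is that no instrument is named.

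The objection does not answer why the test should be chosen after the data are seen, or why a variable used in the main models should be left out when including it costs nothing.

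**Conclusion.** The point holds as an inexpensive improvement. The SAP should replace an unadjusted test, chosen later, with one site-adjusted comparison chosen now. The likely gain is a standard error smaller by about 2.5% to 5% if site explains 5% to 10% of the variance. That becomes about 1% to 4% after the cost of estimating three site terms, and nothing if site is unrelated to use. The gain in pre-specification does not depend on any assumption.

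A site-adjusted regression has one further merit: it tolerates one-year attendance that depends on arm and site together, which a plain two-sample test may not. I put no figure on adding a baseline substance diagnosis. The documents do not say that the MINI records one, and item 7 excludes some dependence, which may narrow its range. Whether substance use differs by site or predicts dropout is likewise not documented. The primary analysis and its conclusion are unaffected.

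**What to change.** In the SAP's last paragraph, name one analysis per outcome:

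- Regress the one-year value on arm and site with robust standard errors, and report the adjusted difference with its confidence interval. If the expected distribution makes a mean unhelpful, name a site-stratified rank test (van Elteren) instead. Either way, fix the choice in the text now, with no reference to the observed distribution.
- Add a baseline substance diagnosis to the regression only if the MINI at time 0 records one, and say so in advance.
- As a sensitivity analysis for participants without a one-year value, use multiple imputation from arm, site, baseline variables and earlier-visit variables. State that its gain is limited, because the outcome itself is never measured earlier.

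Name the instrument or items in Protocol item 13.b at month 12, or record in the SAP where they were collected, so that the two documents agree. If outcome data by arm have already been seen, date the change and label it as made afterwards.

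The cost is a few sentences in the SAP, one table row in the protocol and very little analysis work. No new data collection is needed.
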